1.7 Statistical plan

The feasibility phase is structured similar to a classic 3 + 3 Phase I study. The first six patients will be treated at the targeted dose. Like most Phase I studies, this dose will be considered feasible if <2/6 patients experience attributable DLT. If at least two patients experience attributable DLT, six additional patients will be treated at dose level -1. If fewer than 2 patients experience attributable DLT, that dose will be used in the Randomized Phase II portion of the trial.

The primary endpoint of the Randomized Phase II portion is the complete remission rate. The randomized phase II portion of the study utilizes a group sequential design to test the hypothesis that arm A (nintedanib+chemotherapy) will have a complete response rate of 40% after one cycle of treatment compared to 15% in arm B (Placebo+chemotherapy). Estey, Thall, and David reviewed the outcomes of salvage therapy for AML⁴⁸. They stratified patients based on length of first remission (S1: if greater than 2 years) and whether the therapy was first or subsequent salvage (S2: first remission 1 – 2 years, S3: First remission 0- 1 year, first salvage: S4: First remission 0 – 1 year, receiving > first salvage). CR rates for S2, 3, and 4 were 47%, 14%, and 0. We will not be treating S1 in this protocol. Thus, a 40% response rate appears to be very robust for a mix of S2 to S4 patients. While it is highly unlikely that the control (placebo) arm will have a comparable CR rate, without the control arm the success of the addition of nintedanib will not be clear. Using the group sequential design we will minimize the number of patients receiving placebo. For example, if 0/8 patients in the placebo arm achieve remission, the arm will be stopped for futility. In contrast, if 5/11 patients in the nintedanib arm achieve CR, the study can be declared a success.

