For Phase II, OnCore will be used to randomize the patients by assigning a sequence number that will correspond to the treatment assignment. The list that includes the sequence number with the corresponding treatment assignment will be generated by the study statistician and released only to the research pharmacist at the site. The group sequential design allows termination of either arm at early time points due to either futility or efficacy. In a randomized Phase II trial, each arm is compared to a historic control. The studies are not powered to officially compare the arms. Rather, they serve as “pick the winner” strategies. The null hypothesis is that each arm achieves a 15% response rate. The trial is powered to select an arm (presumably the experimental arm) which achieves a 40% response rate. At the point at which either arm can no longer demonstrate a 40% response rate, the arm is terminated for futility. Each arm is monitored following each accrual beginning with patient 8. The design assumes overall Type I error of 10% (1-sided) and 80% power.

The following table demonstrates the number of responses at each accrual which would stop the trial for either futility (third column) or efficacy (fourth column):

Analysis	Number of included patients	Number of responses to stop for futility	Number of responses to stop for efficacy
1	8	0	4
2	9	1	4
3	10	1	5
4	11	1	5
5	12	2	5
6	13	2	5
7	14	2	6
8	15	2	6
9	16	3	6
10	17	3	7
11	18	3	7
12	19	3	7
13	20	4	7
14	21	4	8
15	22	4	8
16	23	4	8
17	24	5	8

While this is a randomized Phase II study and each arm is ultimately statistically compared to the historical control, the response rates will be qualitatively compared between the two arms in order to get a sense whether the positive signal in the nintedanib arm is strong enough to warrant further development in larger trials.

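### Section 1.7 compares the arms' response rates informally after up to 17 looks per arm but names no estimate that allows for early stopping, so unadjusted rates would overstate the nintedanib effect

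*Combined protocol and SAP*

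**What the plan says.** All of this is in section 1.7 of the combined protocol and SAP.

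- Hypotheses: "The null hypothesis is that each arm achieves a 15% response rate". The target is 40%: "The trial is powered to select an arm (presumably the experimental arm) which achieves a 40% response rate".
- Looks: "Each arm is monitored following each accrual beginning with patient 8". The boundary table runs from 8 to 24 patients, 17 analyses, with a futility count and an efficacy count at each.
- Error rates: "The design assumes overall Type I error of 10% (1-sided) and 80% power".
- Worked example of early success: "if 5/11 patients in the nintedanib arm achieve CR, the study can be declared a success".
- Between the arms: "The studies are not powered to officially compare the arms". Instead, "the response rates will be qualitatively compared between the two arms", so as to form a view on whether the nintedanib signal justifies further, larger studies.

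Neither section 1.7 nor any other section names an estimator, a confidence interval or an adjustment for stopping.

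**The concern.** An arm that stops early for efficacy tends to do so on a run of good results, and an arm that stops early for futility on a run of poor ones. Responses divided by patients treated then tends to be too high in the first case and too low in the second. If nintedanib works and placebo does not, the two errors widen the apparent gap.

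Section 1.7 says that the control arm is there because the contribution of nintedanib would otherwise be unclear. The contrast between the arms is therefore the planned evidence on that contribution. There is no powered between-arm test behind it, so the size of the two rates is what a reader would weigh. With no estimator named, the ordinary reading of a response rate is the raw proportion.

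**Working it through.** **Inputs, all from section 1.7.** Null rate 15%, target 40%. For n = 8 to 24:
- Futility if responses are at or below 0,1,1,1,2,2,2,2,3,3,3,3,4,4,4,4,5.
- Efficacy if responses are at or above 4,4,5,5,5,5,6,6,6,7,7,7,7,8,8,8,8.

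**Assumptions.** The arms are independent, each runs to its own boundary, and every response is known at each look. The outcomes 6/24 and 7/24 fall in neither column. They are counted in the all-outcome averages but not as success.

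**Method.** Let c(n,s) be the number of patient sequences that reach s responses in n patients without stopping earlier. Then c(n,s) = c(n−1,s) + c(n−1,s−1), summing over continuing states only. The probability of stopping at (n,s) is c(n,s)·p^s·(1−p)^(n−s). The mean raw rate is the sum of this probability times s/n. The mean given success is the same sum over efficacy stops, divided by the probability of an efficacy stop.

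**Step 1: the plan's own figures.** The printed table gives power of 82.0% at p = 0.40 (stated 80%) and one-sided error of 5.97% at p = 0.15 (stated 10%). Both lie within the stated limits, although the 10% itself is not reproduced. Repeated looking does not inflate the test.

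**Step 2: the raw rates.**

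| True rate | P(efficacy stop) | Mean raw rate, all outcomes | Mean raw rate given efficacy stop |
|---|---|---|---|
| 15% | 6.0% | 12.7% | 44.7% |
| 25% | 32.4% | 24.5% | 44.8% |
| 30% | 51.0% | 31.1% | 45.6% |
| 40% | 82.0% | 43.0% (0.4305) | 48.8% |

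**Step 3: the difference between arms.**
- True 40% and 15% (25 points), all outcomes: 43.0 − 12.7 = 30.3 points.
- The same, given a nintedanib efficacy stop: 48.8 − 12.7 = 36.1 points.
- True 25% in both arms (no effect), given a nintedanib efficacy stop: 44.8 − 24.5 = 20.3 points.

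**Step 4: is this only selection on success?** A fixed sample of 24, given success, averages 41.9% (success at 7 or more) or 43.4% (8 or more) at a true 40%. Most of the excess up to 48.8% therefore comes from sequential stopping.

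**Step 5: an unbiased estimate.** The uniformly minimum-variance unbiased estimate (UMVUE) at a stopping point is the share of sequences reaching it whose first patient responded. For 5/11, the sequence must stand at 3/9 and then have two responses. Earlier, it stood at 3/8 or 2/8.
- All sequences: C(8,3) + C(8,2) = 56 + 28 = 84.
- First patient responded: C(7,2) + C(7,1) = 21 + 7 = 28.
- Estimate: 28/84 = 33.3%, against 45.5% raw.

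| Stop | Raw | UMVUE |
|---|---|---|
| 4/8 | 50.0% | 50.0% |
| 4/9 | 44.4% | 37.5% |
| 5/11 | 45.5% | 33.3% |
| 5/13 | 38.5% | 30.0% |
| 3/16 (futility) | 18.8% | 27.1% |
| 6/16 | 37.5% | 28.7% |
| 5/24 (futility) | 20.8% | 28.2% |
| 8/24 | 33.3% | 28.3% |

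Over all outcomes the UMVUE averages exactly 15% and 40% at those true rates. Given an efficacy stop at a true 40% it still averages 44.5%.

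**The case against.** **The formal decision is elsewhere.** A reader might infer that the go/no-go decision rests on raw rates, or that 17 looks raise the false-positive risk. The documents support neither. Success is a boundary test against 15%, with exact error 5.97%. The between-arm look is described as qualitative, with no threshold or rule, and that the rates are raw is inferred from silence. This stands, and it confines the point to estimation.

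**The consequence is not documented.** A reader might also infer that the next trial will be under-sized. Nothing says that it would be sized from these rates.

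**The size depends on assumptions.** The 36 points require placebo to run to its own boundary, yet section 1.7 also speaks of the counts stopping the trial. If placebo accrual ends when nintedanib succeeds (equal accrual assumed), the mean raw placebo rate is 14.3% and the difference is 48.8 − 14.3 = 34.5 points. Section 1.5.1 reads response at count recovery or after day 45, with follow-up to day 60, so patients may be enrolled while results are pending. Two such patients (assumed) cut 48.8% to 47.0%, and four cut it to 45.8%. The bias shrinks but remains.

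**The remedy is imperfect.** At a true 40%, 40.6% of trials stop for efficacy at n=8, which is 49.5% of the 82.0% that succeed, and there the UMVUE equals the raw rate. It also brings failing and winning arms close together: 5/24 and 8/24 both give about 28%. Its root mean squared error is no better at 40% (16.7 points against 16.5 raw) or at 15% (11.9 against 11.4), though it is better at 25% (14.4 against 16.2). This stands. It argues for showing both figures, not for replacing one with the other.

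**Conclusion.** The point holds as one about estimation. The rates that section 1.7 compares are biased by its own stopping table, and the plan provides nothing to correct or flag this. Over all outcomes the effect is modest: about +3 points at a true 40%, −2 at a true 15%, and 5 points on the difference. Given an efficacy stop it is larger, at +9 points on the nintedanib rate at a true 40%. It matters most when nintedanib adds little: with 25% in both arms, a nintedanib success still carries an expected raw gap of about 20 points. These figures rest on independent arms, each running to its own boundary, with complete responses at each look.

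A stronger conclusion, that the success declaration is unsound or that raw rates should be discarded, does not follow.

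**What to change.** Add a few lines to section 1.7:

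- For each arm, report the raw CR rate, a bias-adjusted estimate for the printed stopping table (for example the UMVUE) and an exact interval that respects the stopping order.
- Make the between-arm statement with both sets of figures shown, not on raw rates alone.
- State that the adjustment leaves stops at n=8 unchanged, and that after a success stop it reduces the overstatement without removing it (44.5% on average against a true 40%).
- State that the adjusted figures must be recomputed if patients are enrolled beyond the stopping point, and say whether placebo accrual continues once nintedanib has met its efficacy boundary.

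The cost is minor programming and a less favourable reported rate for success stops after n=8. Boundaries, sample size and trial conduct do not change.

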1.8 Patient selection

1.8.1 *Inclusion criteria*

Patient must meet all of the following criteria to be eligible for the study

1/ Patient aged 18y or older

2/ Diagnosis of AML according to WHO 2008 criteria⁴⁹. Therapy related AML may be included if in complete response and off treatment for their prior malignancy for more than 2 years. AML arising after documented MPD are excluded.

3/ Patient must meet one of the following criteria: a/ patient refractory to one or two standard induction regimen b/ patients with a first untreated relapse within 2 years of documentation of clinical remission. Patients relapsing after allogeneic stem cell transplantation are eligible if more than 6 months after transplantation and without sign of active GVHD.

4/ Patient may have been pretreated with intermediate to high dose cytarabine (more than 1000mg/m²/d over 5d) if the day of the last infusion was at least 90 days before inclusion in the study.

5/ ECOG performance status of 2 or less

6/ Patient is willing to participate to the study, has the ability to adhere to the study visit schedule and other protocol procedures, and has the ability to understand and signs an informed consent form.

7/ Women of childbearing potential must agree to use effective contraception without interruption throughout the study and for a further 3 months after the end of treatment;

8/ Men must agree to not conceive during the treatment and to use effective contraception during the treatment period (including periods of dose reduction or temporary suspension) and for a further 3 months after the end of treatment if their partner is of childbearing potential.

1.8.2 *Exclusion criteria*

Any of the following criteria excludes the patient from participating to the study.

- 1/ Patient with documented acute promyelocytic leukemia and/or PML-RAR transcript.
- 2/ Patient relapsing more than 2 years after initial remission.
- 3/ Use of any active treatment for relapse/refractory AML including but not restricted to chemotherapy, targeted agents, hypomethylating agents or investigational drugs. Use of hydroxyurea up to 6g per day for cytoreduction is allowed for a maximum of 30 days prior treatment.
- 4/ Patients with clinical evidences of active CNS disease at inclusion
- 5/ LVEF below 45% or lifetime exposure to anthracyclines over 350mg/m² of daunorubicin equivalent
- 6/ Liver function tests: AST ALT above 2.5 ULN, total bilirubin above 2.5 ULN in the absence of Hemolysis or diagnosis of Gilbert's syndrome
- 7/ Serum creatinine above 2.0mg/dl
- 8/ Any sign of active uncontrolled disease including but not restricted to cardiac disease, infections, hepatitis. Any severe chronic disease potentially interfering with the protocol including HIV infection, active hepatitis B or C. It includes major injuries and/or surgery within the past 4 weeks prior to start of study treatment with incomplete wound healing and/or planned surgery during the on-treatment study period.
- 9/ Documented platelet refractoriness.
- 10/ Patient has a history of GI surgical procedures, non-surgical procedures or conditions that might interfere with the absorption or swallowing of the study drugs.
- 11/ Women who are pregnant, or who are currently breastfeeding
- 12/ Prior treatment with nintedanib or any other VEGFR inhibitor, With the exception of treatment of prior malignancies with a VEGFR inhibitor.
- 13/ Known hypersensitivity to nintedanib, any other trial drug, or their excipients

14/ Persistence of any clinically relevant (CTCAE grade 2 or above) non-haematological toxicities from previous AML therapy

15/ Active alcohol or drug abuse

16/ Any other condition that, according to the investigator, may forbid the administration of the idarubicin+cytarabine regimen

17/ Therapeutic anticoagulation with INR modifying drug or use of antiplatelet therapy (with the exception of low dose aspirin<325mg/d)

18/ Any malignancies requiring active treatment within the past year other than basal cell skin cancer or carcinoma in situ of the cervix. Patients actively treated with hormonotherapy for prostate cancer or breast cancer are eligible.

1.9 Enrollment Procedure

Prior to obtaining signed consent from a patient, the site principal investigator or coordinator must email the project manager to inquire about study space availability. If a slot is available, the potential study participant will complete the consent process. The informed consent process must be completed before any study screening procedures may begin. Following consent patients will have all required screening procedures outlined in Section 10. The site principal investigator or other approved investigator must document that the patient has met all inclusion criteria and has none of the exclusion criteria. Following completion of eligibility testing, eligibility documents will be sent to the YCCI project manager. Examples of required documents are listed in the manual of operations.

Upon review and approval by the Project Manager, the PM will send back the patients' study ID # and dose assignment (for Phase II) to the study team via email. The study team will register the patient into the Clinical Trials Management System, OnCore. During the Phase II portion of the study, the study sites will use OnCore to randomize the patient and receive a sequence # that corresponds to the study arm.

1.10 Assessments

Written informed consent will be obtained from the patient before any study specific procedure is undertaken and documented in the patients' medical record.

Patients will be informed about the study, both verbally and by reviewing the consent form with the study investigator. The patient must be given the opportunity to ask questions and given time to consider his or her participation. The investigator and the patient will both sign and personally date the consent form as confirmation of consent. A copy of the consent form will be given to the patient.

The screening assessments and study procedures apply to both Phase I and Phase II.

1.10.1 Screening period

The screening period is the time preceding registration and includes the 14-day period for performing screening assessments.

The following assessments will be completed within 2 weeks prior to the first dose of study drug:

- Informed Consent
- Medical history,
- Complete physical examination,
- Body weight, height and vital signs,
- ECOG performance status,
- EKG,
- Chest X-ray,
- assess left ventricular ejection fraction (LVEF); using 3D Echocardiogram or the biplane Simpson method.
- Concomitant medication,
- Hematology: Complete Blood Cell Count (CBC) with differential (differential done as per hospital standard of care) entire panel is required at screening
- Serum chemistry: AST, ALT, alkaline phosphatase, total bilirubin, BUN, serum creatinine, glucose, calcium, sodium, potassium, magnesium, chloride, bicarbonate, total protein, albumin, uric acid, LDH, and Beta HCG (women of childbearing potential only)

- Hepatitis B and C, HIV1 and 2 serologies
- Coagulation profile: prothrombin time, activated partial-thromboplastin time, fibrinogen,
- Additional examination when clinically indicated (lumbar puncture, CT-scan, PET CT scan).
- Bone marrow evaluation including a new cytogenetic and molecular characterization at the time of relapse,
- Pharmacodynamic assessment: collection of blood (5 x 4mL) and bone marrow samples (8mL).

The following assessments will be performed just prior to treatment from day – 1 to 1: If these tests are performed within 24 hours of the Cycle 1 Day 1 visit, prior to administration of study drug, they do not need to be repeated on Cycle 1 Day 1, unless otherwise determined by the Principal Investigator.

- Physical examination,
- Body weight,
- ECOG performance status,
- Hematology = CBC with differential (differential done per hospital standard of care)
- Serum chemistry. It includes AST, ALT, alkaline phosphatase, total bilirubin, BUN, serum creatinine, glucose, calcium, sodium, potassium, magnesium, chloride, bicarbonate, total protein, albumin and LDH.
- Coagulation profile: prothrombin time, activated partial-thromboplastin time, fibrinogen,
- Bacterial, fungal and viral cultures of throat, stool and urine, if clinically indicated,
- Pregnancy test (women of childbearing potential only)

1.10.2 Evaluation during treatment period

The treatment period begins Cycle 1 Day 1 and can continue until up to 30 days after the last dose of Nintedanib. The treatment period can include a maximum of 2 (28 day) induction and 2 (28 day) consolidation cycles. If Maintenance therapy is indicated, patients will be followed monthly for the first 12 months and then every three months for the following year (a maximum of 24 months). Number and type of cycle will vary by patient and according to local SOC procedures.

Labs between day 8 and counts recovery can be done +/-2day

The following assessments need to be completed:

- Physical examination daily from day 1 to day 6 and then twice weekly during the induction cycle(s) 1 and 2 (if receiving a second cycle). During consolidation cycle(s) 1 and 2 at day 1, then weekly, and at the end of each cycle.
- ECOG performance status weekly during the first induction cycle and at the end of each cycle thereafter,
- Any adverse event,
- Concomitant medication,
- CBC with differential daily from day 1 to day 5 and then every other day for the first cycle and three times weekly of each cycle thereafter, (differential done as per hospital standard of care) entire panel required at response evaluation
- Serum chemistry daily from day 1-5. Then at a minimum of twice weekly, 3-4 days apart (+/- 2 days) during the first cycle and every other week each cycle thereafter. It includes AST, ALT, alkaline phosphatase, total bilirubin, BUN, serum creatinine, glucose, calcium, sodium, potassium, chloride, bicarbonate, total protein, albumin, LDH and magnesium
- Pregnancy test prior the beginning of each new treatment cycle (women of childbearing potential only)
- Coagulation profile daily from Day 1-5 of cycle 1 and then weekly during the first two cycles: prothrombin time, activated partial-thromboplastin time, fibrinogen,
- Bone marrow evaluation will be performed in patients with complete clearance of blasts in the blood on Day 14 (+/- 1 day) and at the end of cycle 1 Day 28 (+/- 7 days) and decided by local investigator based on count recovery. Threshold: ANC at 1 and PLT at 50,
- Assess LVEF before cycle 2; this can be done any time after Cycle 1 day 14 up to the start of cycle 2, ideally closer to cycle 2 Day 1 using 3D Echocardiogram or the biplane Simpson method.

- Pharmacodynamic assessment: collection of blood (5 x 4mL) and bone marrow samples (5-6mL if a bone marrow aspirate is performed) at day 8, 14 (+/-1d) and at the end of the cycle (in patients with complete clearance of blasts in the blood). Day 8 bone marrow aspirate is optional and will be performed in patients who specifically consented. If patient consents to D8 optional BMBX, start Nintedanib/placebo on afternoon dose after BMBX and continue until D29 morning dose.

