In phase II, patients failing to achieve response based on IWG 2003 AML response criteria after cycle 1 will be unblinded, and all those who had been receiving placebo will be offered a cycle of Nintedanib+ chemotherapy (cross over). Patients in the Nintedanib arm may receive a second induction cycle of Nintedanib. Based on clinical judgement, patients can receive up to 2 cycles of consolidation after induction cycle (s) are complete.

Patients are eligible for allogeneic transplantation as soon as remission is achieved and a donor is identified. All transplant procedures occur off study. For responding patients not eligible for transplantation, maintenance therapy with Nintedanib/Placebo will be provided until documented progression.

Patients should NOT start Cycle 1 day 1 on a Thursday or Friday in order to facilitate sample collection, processing and shipment to Sponsor to avoid weekend deliveries.

[figure not shown]

Figure 2. Global treatment strategy of the Phase II portion of the study

NIN/PLA: Nintedanib/ Placebo, CR: complete response, CRp: CR with incomplete counts recovery. Patients can receive up to 2 induction and 2 consolidation cycles.

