1.5.2 Drug Dose adjustments

1.5.2.1 Criteria for interruption of treatment with nintedanib/placebo

Treatment with nintedanib must be interrupted if any of the criteria listed in Table1 is fulfilled and in the absence of alternative probable cause.

Table 1: Criteria when to interrupt treatment with nintedanib /placebo due to an adverse event

If one criterion is met, nintedanib/placebo must be interrupted

 nausea of CTCAE grade ≥ 3 despite supportive care vomiting of CTCAE grade ≥ 2 despite supportive care diarrhea of CTCAE grade ≥ 2 for more than 3 consecutive days despite supportive care AST and/or ALT elevations of $> 2.5 \times$ ULN in conjunction with bilirubin of $> 1.5 \times$ ULN persisting after repeat testing over a 24-hour period. AST and/or ALT elevations of $> 5 \times$ ULN other non-hematological adverse event of CTCAE grade ≥ 3 considered drug-related

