Diarrhea > grade 2 for more than 7 consecutive days despite anti-diarrheal treatment OR diarrhea > grade 3 despite anti-diarrheal treatment	1st episode
Vomiting ** > grade 2 AND/OR Nausea > grade 3 despite anti-emetic treatment	Reduce dose from 200 mg twice daily to 150 mg twice daily
AST and/or ALT elevations of > 2.5 x ULN in conjunction with bilirubin of > 1.5 x ULN persisting after repeat testing over a 24-hour period. OR AST and/or ALT elevations of > 5x ULN Dose adjustment/reduction will occur per dosing table 3 if Nintedanib is re-started after being held	2nd episode Reduce dose from 150 mg twice daily to 100 mg twice daily
Other non-hematological adverse reaction of > grade 3	3rd episode Stop treatment
Elevation of AST and/or ALT values to > 3 x ULN in conjunction with an increase of total bilirubin to \geq 2 x ULN and ALKP < 2 x ULN	Unless there is an alternative cause established, Nintedanib should be permanently discontinued

*CTCAE: Common Terminology Criteria for Adverse Events

Patients should PERMANENTLY discontinue treatment with nintedanib (BIBF1120) in the event of:

- Intolerable Adverse Events (CTCAE grade 3 or 4) that cannot be managed by dose reduction.
- Withdrawal of informed consent.

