g: Day 8 Bone Marrow aspirate is optional. If patient consents to D8 optional BMBX, start Nintedanib/placebo on afternoon dose after BMBX and continue until D29 morning dose.

h: Twice weekly

i: Weekly

j: Every other day

k: Performed in patients with complete clearance of blasts in the blood

l: (+/- 1 day)

m: All three tests are required at screening, CXR not required at End of Treatment evaluation; 3d Echocardiogram or biplane Simpson method are acceptable methods for obtaining LVEF

n: differential for CBC done as per hospital standard of care (Required at screening, response evaluation and end of treatment visit)

p: (+/- 7 Days) and decided based on count recovery: Threshold: ANC at 1 and PLT at 50

q: AEs and Concomitant Medications will be assessed on an ongoing basis. AE assessment should begin following C1D1 treatment,

Cycles 2, 3 and 4 (Induction or Consolidation) * To be followed if Cycles, 2, 3 and 4 are Induction and/or consolidation cycles, if patient goes to Maintenance refer to Maintenance Calendar

	Day																													END Of Treatment
	1	2	3	4	5	6	7	8	9	10	11	12	13	14	15	16	17	18	19	20	21	22	23	24	25	26	27	28		
Bidimensional Echography ^j	x																													
Con Meds ^o																														
Physical Exam ^c	x	x ^a			x ^g		x ^{g,b}				x ^g			x ^{g,b}			x ^{g,b}			x ^g			x	x						
ECOG PS																													x	x
CBC with differential ^m	x ⁱ		x ⁱ		x ⁱ			x ⁱ		x ⁱ		x ⁱ		x ⁱ		x ⁱ		x ⁱ		x ⁱ		x ⁱ		x ⁱ		x ⁱ		x ⁱ		x
Serum chemistry ^d											x ^l											x ^l					x	x		
Pregnancy testing ^p	x																													
Coagulation Profile ^e				x ^h						x ^h					x ^h						x ^h									
Idarubicin ^f	x	x	x																											
Cytarabine	x	x	x																											
Study Drug (nintedanib/placebo)							x	x	x	x	x	x	x	x	x	x	x	x	x	x	x	x	x	x	x	x	x	x		
AEs ^o																														x
Correlative Studies (Blood& Bone Marrow)																														x
Bone Marrow Evaluation																														x ^k

a: Induction cycle ONLY

b: Weekly for a Consolidation cycle

c: Complete physical exam and vitals including weight, blood pressure, pulse, temperature, respiratory frequency

d: Serum chemistry: AST, ALT, alkaline phosphatase, total bilirubin, BUN, serum creatinine, glucose, calcium, sodium, potassium, magnesium, chloride, bicarbonate, total protein, albumin, LDH,

e: Coagulation profile: prothrombin time, activated partial-thromboplastin time, and fibrinogen

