f: Idarubicin may be dose reduced, replace, or omitted according to total dose of anthracycline received by the patient

g: Twice weekly for an Induction Cycle

h: Weekly; Cycle 2 ONLY

i: Three times weekly

j: Prior to Cycle 2: Any time after Cycle 1 day 14 up to the start of cycle 2; 3d Echocardiogram or biplane Simpson method are acceptable methods for obtaining LVEF

k: Performed in patients with complete clearance of blasts in the blood

l: Every other week

m: differential for CBC will only be done as per hospital standard of care (Required at screening, response evaluation and end of treatment visit)

o: AEs and Concomitant Medications will be assessed on an ongoing basis

p: prior to the start if each new treatment cycle

Maintenance Cycle, End of Treatment & Follow Up

	Maintenance Therapy																				Every 3 months (+/- 7 Days) up to 2 years		
	Monthly (+/- 3 days) for the first 12 months then every 3 months (+/- 7 Days) until disease progression or up to 2 years																						
Month	1	2	3	4	5	6	7	8	9	10	11	12	14	15	16	18	20	21	22	24	End of Treatment	Follow-Up	
Nintedanib ^a	X	X	X	X	X	X	X	X	X	X	X	X	X	X	X	X	X	X	X	X			
Concomitant Medications ⁱ																							
Physical Exam ^b	X	X	X	X	X	X	X	X	X	X	X	X		X		X		X		X	x		
ECOG PS	X	X	X	X	X	X	X	X	X	X	X	X		X		X		X		X	x		
AEs ⁱ																							
CBC with differential ^f	X	X	X	X	X	X	X	X	X	X	X	X	X	X	X								
Serum chemistry ^c	X	X	X	X	X	X		X		X	X		X	X	X		X	x		x			
Pregnancy Testing ^j	X	X	X	X	X	X	X	X	X	X	X	X	X	X	X	X	X	X	X	x ^j	x ^j		
Coagulation Profile ^d	X		X		X																		
EKG, Cardiac Echo ^g																					x		
Bone Marrow Evaluation ^e																					x		
Correlative Studies (Blood & Bone Marrow)																					x		
Hematology, CBC & hemoglobin																					x		
Subsequent anti-cancer therapy, documentation/date of last disease progression/relapse, date of death																						x	

a: Continuous/daily

b: Complete physical exam and vitals including weight, blood pressure, pulse, temperature, respiratory frequency

c: Serum chemistry: AST, ALT, alkaline phosphatase, total bilirubin, BUN, serum creatinine, glucose, calcium, sodium, potassium, chloride, bicarbonate, total protein, albumin,

d: Coagulation profile: prothrombin time, activated partial-thromboplastin time, fibrinogen,

e: Performed in patients with complete clearance of blasts in the blood (+/- 7 Days)

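### Liver chemistry is scheduled by cycle number, so placebo patients who cross over get about 3 scheduled panels in their first nintedanib cycle, against about 6 for patients who start in cycle 1

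*Combined protocol and SAP*

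**What the plan says.** Section 1.10.2 requires chemistry daily on days 1 to 5 of treatment. It continues: "Then at a minimum of twice weekly, 3-4 days apart (+/- 2 days) during the first cycle and every other week each cycle thereafter". The study calendar (1.25.7) agrees. The cycle 1 chemistry row is footnoted as twice weekly, and the row for cycles 2 to 4 carries "l: Every other week". A single calendar serves all later cycles; its heading reads "To be followed if Cycles, 2, 3 and 4 are Induction and/or consolidation cycles".

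Under Section 1.5.1, phase II "patients failing to achieve response based on IWG 2003 AML response criteria after cycle 1 will be unblinded", and those found to have been on placebo are offered nintedanib with chemotherapy. Study drug is given on days 8 to 28 of each 28-day cycle.

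Several safety rules act on the liver results. Section 1.5.2.1 says "Treatment with nintedanib must be interrupted if any of the criteria listed in Table1 is fulfilled", and Table 1 includes AST/ALT and bilirubin thresholds. Table 4 sets dose reductions on the same thresholds and permanent discontinuation for "Elevation of AST and/or ALT values to > 3 x ULN in conjunction with an increase of total bilirubin to" at least twice ULN with alkaline phosphatase below twice ULN, unless another cause is established. Section 1.19.7 makes two liver patterns events of special interest. The at-least-weekly testing in 1.25.5 begins once an elevation has been found.

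**The concern.** Testing less often after cycle 1 makes sense for a patient who has already taken nintedanib under close testing. A crossover patient has not. That patient's cycle 2 is a first exposure, but the schedule treats it as a second.

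The protocol names the liver as the main site of dose-limiting toxicity for nintedanib. Section 1.14.1 says that grade 3 enzyme rises in the phase II trials came early after the start of treatment. The Table 1 and Table 4 rules can act only once a result exists. With fewer panels, a patient past a threshold would on average be found later, unless an unscheduled test is done. The other scheduled cycle 2 checks (physical examination twice weekly in induction, blood counts three times weekly, coagulation weekly) do not measure AST, ALT or bilirubin. What is at stake is patient safety in a small group, not the randomised comparison.

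**Working it through.** The plan states no panel count, so there is no figure of its own to reproduce.

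**Inputs.** Dosing on days 8 to 28 is 21 days, or 42 twice-daily doses (1.5.1). Cycle 1 spacing is 3 to 4 days, with +/- 2 days allowed (1.10.2). The cycle 2 to 4 chemistry row has two every-other-week marks, one end-of-cycle mark and one End of Treatment mark (1.25.7). By column position the first three fall near days 11-12, 22-23 and 27-28. The table lost a column in text extraction, so these days are an assumption.

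**Panels in the dosing window**
- Cycle 1 starter: 21 / 3.5 = 6.
- Crossover patient, by the calendar: 3.
- Crossover patient, by the text of 1.10.2 alone: every 14 days with the starting day unspecified gives 1 (first panel on days 1 to 7) or 2 (days 8 to 14).

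**Longest gap**
- Cycle 1: 4 days nominal, or 4 x 2 = 8 doses. With one panel 2 days early and the next 2 days late, 4 + 2 + 2 = 8 days.
- Cycle 2, by the calendar: 22 - 11 = 11 days nominal, or 22 doses.

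**Mean wait from onset to next panel.** For onset uniform over consecutive gaps g, the mean wait is (sum of g squared) / (2 x sum of g).
- Cycle 1: 3.5 / 2 = 1.75 days.
- Cycle 2, marks on days 11, 22, 27 (gaps 3, 11, 5): (9 + 121 + 25) / (2 x 19) = 4.1 days.
- Cycle 2, marks on days 12, 22, 28 (gaps 4, 10, 6): (16 + 100 + 36) / (2 x 20) = 3.8 days.

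If onset is uniform over the first nintedanib week, days 8 to 15 (my assumption for 'early'):
- Marks on days 11 and 22: (3 x 1.5 + 4 x 9) / 7 = 5.8 days.
- Marks on days 12 and 22: (4 x 2 + 3 x 8.5) / 7 = 4.8 days.
- Cycle 1 stays at 1.75 days.

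**How many patients.** Section 1.7 gives stopping boundaries from patient 8 to patient 24 in each arm; for example, "if 0/8 patients in the placebo arm achieve remission, the arm will be stopped for futility". An exact recursion on that table, for one arm alone and stopping at or beyond a boundary, gives:

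| CR rate | Expected arm size | Expected without CR |
|---|---|---|
| 10% | 9.8 | 8.8 |
| 15% | 11.3 | 9.6 |
| 20% | 12.6 | 10.0 |
| 30% | 13.2 | 9.2 |

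At 15%, the chance of stopping by patient 12 is 0.80 and of reaching 24 is 0.06. Crossover depends on failing to respond, and CRi, PR or MLFS may also count as response. I therefore take non-response as 60% to 85% (assumption): 11.27 x 0.60 = 6.8 to 11.27 x 0.85 = 9.6, or about 7 to 10 candidates. If the arm filled to 24 the range would be 24 x 0.60 = 14 to 24 x 0.85 = 20. Deaths, day-60 removals and refusals lower these figures. Enrolment while responses are pending could raise the expected number somewhat.

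**The case against.** The strongest reply is that this gap will seldom bite. Section 1.5.1 describes the regimen as given in an inpatient stay averaging about 5 weeks under local standard of care, and inpatients on intensive chemotherapy are likely to have extra chemistry drawn. The cycle 1 frequency is worded as a minimum, and that wording can be read as covering later cycles too. Adverse events are assessed continuously, and coagulation stays weekly in cycle 2. All this stands as mitigation, but none of it requires AST, ALT or bilirubin at a stated interval, and earlier discharge is allowed. A reader might infer that a crossover patient would go on dosing until the next scheduled panel. That is the worst case, not the expected course.

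The evidence on timing is also indirect. The early rises were seen in solid-tumour monotherapy trials, mostly at 250 mg bid, and were reversible. The dose here is 200 or 150 mg bid, and 'early' is not defined. The documents give no event rate for this combination. If 5% to 15% of candidates crossed a threshold (illustration only), 7 x 0.05 = 0.35 to 10 x 0.15 = 1.5 patients would be affected. This limits the weight of the point. It does not explain why a first exposure in cycle 2 should be tested less than a first exposure at the same dose in cycle 1.

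Finally, the text and the calendar agree with each other, so this is a design choice and not a contradiction.

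**Conclusion.** The point holds as a minor safety-monitoring gap. First nintedanib exposure after crossover has about 3 calendar panels against about 6, a longest nominal gap of about 11 days against 4 (up to 8 in cycle 1 if the window is fully used), and a mean wait of about 4 days against 1.75, or about 5 to 6 days if onset falls in the first nintedanib week. These figures rest on approximate calendar days and on protocol minimums.

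Three stronger readings are not supported:

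- **One or two panels and a 14-day gap.** This follows from the text alone with an unspecified starting day. The calendar, which sites work from, adds an end-of-cycle panel and brings the gap to about 11 days.
- **Undetected liver injury is to be expected.** The documents give no rate from which to say so, and inpatient care makes unscheduled testing likely.
- **The efficacy result is compromised.** The primary endpoint is remission after cycle 1, and crossover comes later, so the randomised cycle 1 comparison is untouched.

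**What to change.** Add one sentence to 1.10.2, and the same text as a footnote to the serum chemistry row of the cycle 2 to 4 calendar:

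> For patients who cross over from placebo to nintedanib, serum chemistry in the first nintedanib cycle is done at least twice weekly, 3-4 days apart (+/- 2 days), from day 8 to day 28.

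The rule should name crossover patients only. They are already unblinded, so sites know whom it covers and no blind is broken. A rule keyed to first nintedanib use in any cycle would reach beyond that group.

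The cost is 6 - 3 = 3 to 6 - 1 = 5 extra panels per crossover patient, drawn with blood counts already taken three times weekly. In total that is about 7 x 3 = 21 to 10 x 5 = 50 panels at the expected arm size. Nothing changes in the analysis or the sample size.
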